7.2. FOLFOX6 (m)

Drugs in this combination are commercially available. These drugs will be formulated, packaged, labeled and stored according to the procedures indicated by the local manufacturer, the supplier and the center. Consult the product data sheet for information on packaging and formulation, labeling, storage, preparation, supply / return, and counting of the combination.

As they are commercialized drugs of habitual use in the study pathology, the supply will be carried out through the usual channels of the National Health System, with the prior favorable opinion of the CEIC and the approval of the Center's Directorate.

Prior to administration of FOLFOX6 (m) chemotherapy, the investigator or designee will review the subject's hematology and biochemical tests, liver function tests, and the incidence of hematologic or non-hematologic toxicities, and follow the parameters of sections 7.2.2 and 7.2.3 to determine if the treatment is adequate.

7.2.1 Premedication FOLFOX6 (m)

Prior to administration of FOLFOX6 (m), all subjects should receive antiemetic products (eg, oral or IV dexamethasone and 5-hydroxytryptamine3 [5-HT3] receptor antagonists). Antiemetics should be administered on the day of treatment, starting at least 30 minutes before the administration of FOLFOX6 (m). Alternative and additional antiemetics may be used, when clinically indicated, at the discretion of the investigator, or in accordance with standard institutional practice.

Single-arm, multicenter, prospective phase II clinical trial for biomarker validation in patients with advanced and / or metastatic colorectal cancer with non-mutated KRAS gene treated with chemotherapy plus biweekly cetuximab as first-line therapy

7.2.2 FOLFOX6 (m)

Administration of FOLFOX6 (m) chemotherapy will begin on day 1 of each treatment cycle.

The FOLFOX6 (m) regimen will be administered every 2 weeks (+/- 3 days), as follows:

Table: Scheme FOLFOX6 (m)

| Drug | Dose | Day | Administration |
|--------------|-----------------------|-----|--|
| Oxaliplatin | 85 mg/m ² | 1 | Infusion i.v. of 85 mg / m ² of oxaliplatin in 250-500 ml of D5W and infusion i.v. 400 mg / m ² leucovorin racemate (or 200 mg / m ² l-LV) in D5W, both administered over 120 minutes (\pm 15 minutes) a at the same time in separate bags using a Yc line |
| Leucovorin | 200 mg/m ² | 1 | |
| Fluorouracil | 400 mg/m ² | 1 | Bolus IV |

aExtension of the oxaliplatin infusion time from 2 to 6 hours is allowed, at the discretion of the investigator, to mitigate acute toxicities. It is not necessary to change the duration of 5-FU and leucovorin infusions.

b At the discretion of the investigator, leucovorin and oxaliplatin may be administered sequentially according to standard treatment and local regulations.

cOxaliplatin is not compatible with normal saline or 5-FU. The infusion line should be thoroughly cleaned with D5W before and after 5-FU administration.

[figure not shown]

Figure 2. FOLFOX6 (m) chemotherapy administration schedule

Single-arm, multicenter, prospective phase II clinical trial for biomarker validation in patients with advanced and / or metastatic colorectal cancer with non-mutated KRAS gene treated with chemotherapy plus biweekly cetuximab as first-line therapy

Every 2 weeks a new cycle of FOLFOX6 (m) treatment will be repeated, although it will not be administered to subjects with ANC $<1.5 \times 10^9$ cells / L, or if the platelet count is $<75 \times 10^9$ / L, if the skin toxicity, stomatitis or diarrhea have not recovered to grade ≤ 1 , or if fatigue has not recovered to grade ≤ 2 . A delay of up to 4 weeks is allowed to start a new course of treatment for resolution of the toxicities. If treatment with one component of the FOLFOX6 (m) regimen (for example, 5-FU / leucovorin or oxaliplatin) is delayed, the other component is also delayed in the same way, so that both therapies can be administered together on day 1 of each. 2 week cycle.

In the event that oxaliplatin administration is interrupted for any reason before 6 months of treatment have elapsed or there is progression of the disease, treatment with 5-FU / leucovorin and cetuximab can continue to be administered once every 14 days (± 3 days) until disease progression or intolerance to study treatment.

In no case can a patient be kept under study with oxaliplatin alone, or in combination with cetuximab.

If the discontinuation of FOLFOX6 (m) chemotherapy is ≤ 6 weeks from the previous cycle, if the subject has recovered from toxicities, as noted above, and if the disease has not progressed, FOLFOX6 chemotherapy should be restarted (m) with or without cetuximab with the doses specified in Tables 2, 3 and 4. If the interruption of FOLFOX6 (m) chemotherapy is > 6 weeks but the subject has recovered from toxicities and the disease has not progressed, staff The sponsor of the study should review the case together with the investigator to determine if the treatment should be resumed.

7.2.3 Dose levels and dose modification guidelines for the FOLFOX6 (m) regimen

The toxicity of FOLFOX6 (m) in subjects should be closely monitored. Doses of 5-FU and oxaliplatin can be adjusted according to the individual tolerance of each subject. The leucovorin dose will remain fixed at 400 mg / m² of racemate (d, l-leucovorin) or 200 mg / m² of l-leucovorin. Table 2 to 4 shows recommended dose levels and guidelines. of dose modification, due to neurological and non-neurological toxicity, of both oxaliplatin and 5-FU.

Table 3 describes the recommended dose reductions for non-neurologic toxicity.

Table 3. Dose reductions of FOLFOX6 (m): non-neurological toxicity

| | Initial dose | Dose - 1 | Dose - 2 |
|---------------|-------------------------|-------------------------|-------------------------|
| Oxaliplatin | 85 mg/m ² | 65 mg/m ² | 50 mg/m ² |
| 5-FU Bolus | 400 mg/m ² | 320 mg/m ² | 240 mg/m ² |
| 5-FU Infusion | 2.400 mg/m ² | 1.900 mg/m ² | 1.500 mg/m ² |

Single-arm, multicenter, prospective phase II clinical trial for biomarker validation in patients with advanced and / or metastatic colorectal cancer with non-mutated KRAS gene treated with chemotherapy plus biweekly cetuximab as first-line therapy

Table 4 below describes the recommended dose modifications at the start of each subsequent therapy cycle. All dose modifications must be based on the worst preceding toxicity.

Table 4 Dose modifications

Table 4 Dose modifications

| Toxicity | Dose level for subsequent cycles | In the moment of retreatment |
|---|---|--|
| Based on the toxicity of the interval** | | |
| Absence of toxicity | Maintain the dose level | Maintain the dose level |
| Neutropenia (ANC) | | |
| Grade 1 (ANC < LIN – 1,5 x 10 ⁹ /L) | Maintain the dose level | If ANC <1.5 x 10 ⁹ / L at the beginning of the cycle, suspend and check weekly, then treat according to the toxicity of the interval. |
| Grade 2 (ANC 1,5 x 10 ⁹ /L - 1,0 x 10 ⁹ /L) | Maintain the dose level | If ANC <1.5 x 10 ⁹ / L after 4 weeks, discontinue treatment. |
| Grade 3 (ANC 1,0 x 10 ⁹ /L – 0,5 x 10 ⁹ /L) | Reduce 1 dose level of 5-FU and OXAL | |
| Grade 4 (ANC < 0,5 x 10 ⁹ /L) | Reduce 1 dose level of 5-FU and OXAL | |
| Thrombocytopenia | | |
| Grade 1 (PLT < LIN - 75,0 x 10 ⁹ /L) | Maintain the dose level | If PLT <75.0 x 10 ⁹ / L at the beginning of the cycle, suspend and check weekly and then treat according to the toxicity of the interval. |
| Grade 2 (PLT 75,0 x 10 ⁹ /L - 50,0 x 10 ⁹ /L) | Maintain the dose level | If PLT <75.0 x 10 ⁹ / L after 4 weeks, discontinue treatment. |
| Grade 3 (PLT 50,0 x 10 ⁹ /L - 25,0 x 10 ⁹ /L) | Reduce 1 dose level of 5-FU and OXAL | |
| Grade 4 (PLT < 25,0 x 10 ⁹ /L) | Reduce 1 dose level of 5-FU and OXAL | |
| Febrile neutropenia | | |
| ANC < 1,0 x 10 ⁹ /L (neutropenia of grade 3 o 4) y fever ≥ 38,5 °C | Reduce 1 dose level of 5-FU and OXAL | |

Single-arm, multicenter, prospective phase II clinical trial for biomarker validation in patients with advanced and / or metastatic colorectal cancer with non-mutated KRAS gene treated with chemotherapy plus biweekly cetuximab as first-line therapy

Other hematologic toxicities

Dose modifications for leukopenia at the start of subsequent cycles of therapy and at the time of retreatment are also based on the NCI toxicity criteria (CTC version 3.0) and are the same as those recommended above for neutropenia.

Diarrhea

| | | |
|---------|---------------------------------------|--|
| Grade 1 | Maintain the dose level | For grade 2 diarrhea at the start of the cycle, suspend and check weekly, then treat according to interval toxicity. |
| Grade 2 | Maintain the dose level | |
| Grade 3 | Reduce 1 dose level of 5-FU and OXAL | If grade 2 diarrhea persists after 4 weeks, discontinue treatment. |
| Grade 4 | Reduce 1 dose level of 5-FU and OXAL. | |

Other non-hematologic toxicities^{1,2}

Dose modifications for other non-hematologic toxicities at the beginning of subsequent therapy cycles and at the time of retreatment are also based on the NCI toxicity criteria (CTC version 3.0) and are the same as those recommended above for diarrhea.

The LV dose will not be adjusted due to toxicity. It should remain at 400 mg / m² racemate (or 200 mg / m² L-LV) in all cycles. LV should be given just before each 5-FU dose; thus, if 5-FU is delayed, LV will also be delayed.

* Common toxicity criteria from the National Cancer Institute (CTC version 3.0).

** Refers to the starting dose used in the previous cycle.

1 In case of mucositis / stomatitis, reduce only the dose of 5-FU, not that of oxaliplatin.

2 Exceptions: alopecia, fatigue, anorexia, nausea / vomiting if they can be controlled with antiemetics, viral infections.

Table 5 describes the recommended dose modifications for oxaliplatin, based on the duration of neurotoxicity associated with oxaliplatin.

Table 5. Dose modification rules due to neurotoxicity associated with oxaliplatin

| Toxicity (grade) | Toxicity duration | Persistente (not resolved between cycles) |
|---|-------------------|--|
| | 1 - 7 days | > 7 days |
| Paresthesias / dysesthesias ¹ of short duration that resolve and do not interfere with function (grade 1) | No change | No change |

Single-arm, multicenter, prospective phase II clinical trial for biomarker validation in patients with advanced and / or metastatic colorectal cancer with non-mutated KRAS gene treated with chemotherapy plus biweekly cetuximab as first-line therapy

| | | | |
|--|--|--|--|
| Paresthesias / dysesthesias interfering with function but not activities of daily living (ADL) (grade 2) | No change | No change | Decrease to 65 mg/m ² |
| Paresthesia / dysesthesia with pain or functional impairment that also interferes with ADL (grade 3) | 1st time: decrease to 65 mg/m ² 2nd time: decrease to 40 mg/m ² | DISCONTINUE | DISCONTINUE |
| Persistent paraesthesia / dysesthesia incapacitating or life-threatening (grade 4) | DISCONTINUE | DISCONTINUE | DISCONTINUE |
| Laryngopharyngeal dysesthesias | No change | Increase the duration of the infusion to 6 hours | Increase the duration of the infusion to 6 hours |

¹ May be induced by cold.

Every 2 weeks a new cycle of FOLFOX6 (m) treatment will be repeated, although it will not be administered to subjects with ANC <1.5 x 10⁹ cells / L, or if the platelet count is <75 x 10⁹ / L, if the skin toxicity (not related to cetuximab), stomatitis or diarrhea have not recovered to grade ≤ 1 , or if fatigue has not recovered to grade ≤ 2 . A delay of up to 4 weeks is allowed to start a new cycle of treatment for the resolution of toxicities. If treatment with one component of the FOLFOX6 (m) regimen (for example, 5-FU / leucovorin or oxaliplatin) is delayed, the other component is also delayed in the same way, so that both therapies can be administered together on day 1 of each 2 week cycle.

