7.1.1. Dosage

Before the first infusion, the patient should be administered an antihistamine and a corticosteroid.

This premedication is recommended for all subsequent infusions.

Cetuximab will be administered every 2 weeks, the dose is 500 mg / m².

In reference to the dosage or modifications of the recommended dose of concomitantly used chemotherapeutic agents, consult the SmPC of these drugs. They should not be administered until one hour after the end of the cetuximab infusion.

Biweekly cetuximab treatment should be continued until underlying disease progresses.

Once a dose reduction has been made, a dose escalation will not be allowed in subsequent cycles.

In no case can the patient be kept in the study with Oxaliplatin or Irinotecan in monotherapy, or in combination with cetuximab without 5-FU.

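### Protocol 7.2.3: fixed oxaliplatin doses for neurotoxicity do not fit the stepwise levels once a patient is already reduced, and the rules on late recovery from toxicity are not reconciled

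*Protocol*

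**What the plan says.** **Dose levels.** Section 7.2.3 contains "Table 3. Dose reductions of FOLFOX6 (m): non-neurological toxicity", which lists oxaliplatin at 85, 65 and 50 mg/m². Table 4 moves patients along that list. For grade 3–4 neutropenia, thrombocytopenia or diarrhoea, and for febrile neutropenia, it says "Reduce 1 dose level of 5-FU and OXAL". Its footnote ties the rule to the dose in use: "Refers to the starting dose used in the previous cycle".

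**Fixed doses.** Table 5 of the same section deals with oxaliplatin neurotoxicity. Persistent grade 2 reads "Decrease to 65 mg/m"². Grade 3 lasting 1–7 days goes to 65 mg/m² the first time, and then "2nd time: decrease to 40 mg/m"². Grade 3 of longer duration or persisting between cycles stops oxaliplatin.

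**No escalation.** Section 7.1.1, headed as cetuximab dosing, states: "Once a dose reduction has been made, a dose escalation will not be allowed in subsequent cycles".

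**Delay and stopping.** Sections 7.2.2 and 7.2.3 both allow a new cycle to be delayed by at most 4 weeks. Table 4 stops treatment if neutrophils or platelets are still below threshold at that point, and for diarrhoea it says "If grade 2 diarrhea persists after 4 weeks, discontinue treatment". Section 7.2.2 measures interruption from the previous cycle. Up to 6 weeks, a recovered patient without progression is restarted. Beyond 6 weeks, the sponsor's staff "should review the case together with the investigator to determine if the treatment should be resumed". Sections 7.3.2 and 7.3.3 (Table 7) set out the same pair of rules for FOLFIRI.

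**The concern.** One scheme is relative to the current dose and the other is absolute. They agree only while the patient is on the starting dose. A patient who has already been reduced for a blood count or diarrhoea and then develops neurotoxicity, or the reverse, falls where the tables do not give a workable instruction. Protocol section 4.1 says that neutropenia and sensory neuropathy are each more frequent with this regimen than with 5-FU and leucovorin alone, so the overlap is foreseeable, although no rate is given.

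The delay rules raise a smaller question. A patient who recovers late is covered by an instruction to stop and also by a review that may resume treatment.

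Safety is the first thing at stake. A first short grade 3 episode that interferes with daily activities can leave oxaliplatin unchanged. The second is classification. The SAP (6.5.1.3 and 6.5.1.5) removes significant protocol deviations from the efficacy analysis, and SAP Table 5 has a category for incorrect dosing. The documents do not say whether a dosing deviation counts as significant, but deviations cannot be coded consistently against rules that do not agree, across about 30 centres (Protocol 5.2).

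**Working it through.** The plan states no figure to reproduce here. The check compares each Table 5 target with each oxaliplatin dose that the protocol's own tables can produce, and then puts the two time limits on one clock.

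**Inputs.** Levels 85, 65 and 50 mg/m² (Table 3). Targets 65 and 40 mg/m² (Table 5). Two-week cycle with a ±3-day window, 4-week maximum delay and 6-week limit (sections 7.2.2 and 7.2.3). The Table 5 header is damaged in the extracted text. Its columns are read as 1–7 days, more than 7 days, and persistent.

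**Doses.** Change = target − current; percentage = change / current.

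| Current dose | Target 65 (first grade 3 of 1–7 days, or persistent grade 2) | Target 40 (second grade 3 of 1–7 days) | One level down (Table 4) |
|---|---|---|---|
| 85 | −20 (20/85 = 23.5%) | −45 (45/85 = 52.9%) | 65 |
| 65 | 0 (0%) | −25 (25/65 = 38.5%) | 50 |
| 50 | target 15 above current | −10 (10/50 = 20%) | Table 3 lists no lower level |
| 40 | target 25 above current | 0 | undefined: 40 is not in Table 3 |

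A patient can be at 65 or 50 after one or two Table 4 reductions. A patient reaches 40 only through the second-episode cell of Table 5, so at 40 the relevant 65 target is the one for persistent grade 2.

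The table gives three results:
- At 65, the neurotoxicity instruction is empty.
- At 50, it tells the investigator to go down to a dose that is higher, so it cannot be carried out.
- At 40, a later grade 3–4 haematological toxicity calls for a one-level step from a dose that is not a level.

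Nothing else in 7.2.3 supplies the link. The section says that Tables 2 to 4 cover both kinds of toxicity, and 7.2.2 restarts patients at the doses in Tables 2, 3 and 4. Neither reference includes Table 5, where the neurotoxicity doses stand.

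**Timing.** Cycle + maximum delay = 2 + 4 = 6 weeks from the previous cycle. With the ±3-day window this is (14 − 3 + 28)/7 = 5.6 to (14 + 3 + 28)/7 = 6.4 weeks. The 4-week and 6-week limits therefore meet and do not conflict as limits.

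The mismatch begins after that point. Take a patient whose neutrophils recover in the fifth week of delay, about 2 + 5 = 7 weeks after the last cycle. Under Table 4 this patient had not recovered at 4 weeks, so treatment is discontinued. Under 7.2.2 the same patient has recovered, has not progressed and is beyond 6 weeks, so the case goes to review. Neither place names the other as an exception.

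**The case against.** **On the doses.** The section calls its tables recommendations and guidelines, lets 5-FU and oxaliplatin follow individual tolerance, bases changes on the most severe toxicity so far, and section 7.1.1 refers chemotherapy dose changes to the product information. Table 3 is labelled non-neurological, so separate neurotoxicity doses may be deliberate. This shows that investigators have latitude, and that stands. It does not say what the tables mean at 65, 50 or 40 mg/m².

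A reader might infer that the protocol orders an increase at 50 mg/m². The documents do not support that. The cell is worded as a decrease, so it is contradictory there, and no text sends a patient from 40 up to 50. The no-escalation sentence would also bar a rise if it covers chemotherapy. It sits in the cetuximab section but close to a sentence about oxaliplatin, irinotecan and 5-FU, so its reach is unclear.

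The grade 3 problem is confined to episodes of 1–7 days. Longer or persistent grade 3 neurotoxicity is a stop, and a second short episode has a lower target.

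**On the delay.** A reader might infer that 4 weeks and 6 weeks clash, or that restart after 6 weeks is granted. Neither holds: the limits coincide, and section 7.2.2 offers only a review. The protocol also uses discontinuation for temporary stops (sections 7.1.5 and 7.2.2) and usually marks permanent ones as such, so Table 4 need not be final. The review clause can also serve cases outside Table 4's stop rule, since its footnote excepts fatigue and some other toxicities and section 7.5 allows discussion of restart after unplanned surgery. All of this narrows the point. What remains is the patient with delayed recovery of counts or diarrhoea, for whom both texts apply.

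**On consequence.** PFS follow-up continues after treatment stops (sections 5.1 and 10.2.1), and nothing in the documents links these cases to biomarker group. A claim that the primary comparison is biased would go beyond the documents.

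**Conclusion.** The point holds in a limited form and should be corrected. Table 5's fixed oxaliplatin doses work from 85 mg/m² (a 23.5% reduction at the first step). They give no reduction from 65, are contradictory at 50, and leave Table 4 undefined at 40. Separately, for delays beyond 6 weeks from the previous cycle, the stop in Table 4 and the review in section 7.2.2 overlap without a stated order. FOLFIRI has the same gap.

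This rests on the tables as extracted, on the column reading given above, and on Table 4 reductions remaining in force when neurotoxicity occurs. The number of patients in these situations is not given and cannot be derived. The consequence is for safety instructions and the coding of dosing deviations. No effect on the PFS result is shown.

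**What to change.** The sponsor should reconcile Tables 3, 4 and 5 of Protocol section 7.2.3, together with the no-escalation sentence in 7.1.1, so that the instruction is defined and consistent for patients already on a reduced oxaliplatin dose. The scope of that sentence should be stated. The sponsor should also reconcile the 4-week delay, the Table 4 stop and the review clause in sections 7.2.2 and 7.2.3, and the matching text in 7.3.2 and 7.3.3, on non-recovery after 4 weeks. Which dose or rule is right is for the sponsor to decide.

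The cost is protocol wording, with no added procedures or patients. The SAP records the last patient as completed in June 2017. For this trial, the practical use is therefore to document which reading was applied when dosing deviations were classified.

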7.2.4 Stopping FOLFOX6 chemotherapy (m)

Subjects will be allowed to receive treatment with FOLFOX6 (m) for up to 6 months or until disease progression, or until unacceptable toxicities and / or consent is withdrawn. If patients do not show progression after 6 months of treatment with FOLFIRI (m) or FOLFOX6 (m), they will continue receiving biweekly cetuximab as monotherapy until progression.

If FOLFOX6 (m) chemotherapy is discontinued before 6 months of treatment or disease progression e.g. due to FOLFOX-6 (m) toxicity, the subject may continue to receive cetuximab monotherapy every 14 days (+/- 3 days) until you develop disease progression or are unable to tolerate the investigational product.

The disease of all subjects will be reassessed after 12 weeks \pm 1 week for the period the patient continues in the trial until progression.

Tumor evaluation will be performed on subjects who have withdrawn from the study for reasons other than radiographically documented disease progression. All these subjects should be monitored for disease progression (revised RECIST 1.1 criteria) every 12 weeks +/- 1 week until disease progression or end of study.

7.3 FOLFIRI (m)

Drugs in this combination are commercially available. These drugs will be formulated, packaged, labeled and stored according to the procedures indicated by the local manufacturer, the supplier and the center. Consult the product data sheet for information on packaging and formulation, labeling, storage, preparation, supply / return, and counting of the combination.

As they are commercialized drugs of habitual use in the study pathology, the supply will be carried out through the usual channels of the National Health System, with the prior favorable opinion of the CEIC and the approval of the Center's Directorate.

Prior to the administration of FOLFIRI (m) chemotherapy, the investigator or his / her designee will analyze the subject's hematology and biochemical tests, liver function tests, and the incidence of hematologic or non-hematologic toxicities, and follow the parameters of sections 7.3.2 and 7.3.3 to determine if the treatment is adequate.

7.3.1 Premedication FOLFIRI (m)

Prior to administration of FOLFIRI (m), all subjects should receive antiemetic products (eg, oral or IV dexamethasone and 5-hydroxytryptamine3 [5-HT3] receptor antagonists). Antiemetics should be administered on the day of treatment, beginning at least 30 minutes before FOLFIRI (m) administration. Alternative and additional antiemetics may be used, when clinically indicated, at the discretion of the investigator, or in accordance with standard institutional practice.

